7.2.3.1 Sensitivity Analyses

Currently no sensitivity analysis is planned for the primary endpoint. Any additional sensitivity analysis will be described in the TSAP.

7.2.3.2 Subgroup Analyses

No subgroup analysis is planned for the primary endpoint.

7.2.3.3 Supplementary Analyses

No supplementary analysis is planned for the primary endpoint.

7.2.4 Secondary objective analyses

Pathological response (PR) will be assessed as per Mandard tumor regression grading system ([R21-1544](#)). The study will apply a Bayesian framework to calculate the posterior probability of PR rate for each arm separately. The 95% credible interval of the PR rate will be constructed along with observed PR (naïve estimate) and corresponding 95% confidence interval. In addition, at the final analysis, posterior probability, for each arm, that the PR rate is at least 15% will be calculated (i.e., suggesting that drug is efficacious) under the beta-binomial model with a weakly informative prior: Beta (0.15, 0.85).

Any additional analysis (including sensitivity analysis) to assess pathological responses will be separately described in the Trial Statistical Analysis Plan (TSAP).

Time from administration of trial treatment to surgery will be calculated as [Date of surgery – Date of first treatment administered + 1]. Time from administration of trial therapy to surgery will be summarized descriptively.

Radiographic response will be summarized descriptively along with 95% confidence interval.

7.2.5 Further objective analyses

The study will employ exploratory biomarker analyses to address modulation of key MoA and prognostic biomarkers as supportive evidence for pharmacodynamic response to the treatment. Refer to section 2.2.2 for all the proposed further endpoints.

In addition, retrospective and exploratory subgroup analyses for safety and efficacy would be done for [REDACTED]

[REDACTED] All the subgroup analysis will be summarized descriptively.

By nature, the biomarker analysis would be rather descriptive than quantitative. Thus, the biomarker analysis focuses on detection of significant modulation of those MoA biomarkers from baseline upon one cycle of ezabenlimab/BI 765063 combination treatment. More details on the analyses of further endpoints will be specified in TSAP.

7.2.6 Safety analyses

Adverse events will be coded using the Medical Dictionary for Drug Regulatory Activities (MedDRA). Standard BI summary tables and listings will be produced. All adverse events with an onset between start of treatment and end of the follow-up period, a period of 90 days after the administration of trial medication, will be assigned to the on-treatment period for evaluation.

All treated patients will be included in the safety analysis. In general, safety analyses will be descriptive in nature and will be based on BI standards. No hypothesis testing is planned.

Statistical analysis and reporting of adverse events will concentrate on treatment-emergent adverse events, i.e. all adverse events occurring between start of treatment and end of the follow up period. Adverse events that start before first drug intake and deteriorate under treatment will also be considered as 'treatment-emergent'.

Frequency, severity, and causal relationship of adverse events will be tabulated by system organ class and preferred term after coding according to the current version of the Medical Dictionary for Drug Regulatory Activities (MedDRA) at database lock (DBL).

Laboratory data will be analysed both quantitatively as well as qualitatively. The latter will be done via comparison of laboratory data to their reference ranges. Values outside the reference range as well as values defined as clinically relevant will be summarised. Treatment groups will be compared descriptively with regard to distribution parameters as well as with regard to frequency and percentage of patients with abnormal values or clinically relevant abnormal values.

Vital signs or other safety-relevant data observed at screening, during the course of the trial and at the end-of-trial evaluation will be assessed with regard to possible changes compared to findings before start of treatment.

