2.1.2 Primary endpoint(s)

The primary endpoint is a composite endpoint which estimates proportion of patients with at least one occurrence of a safety or feasibility event. The detailed definitions of safety and feasibility are as follow.

Safety

Safety is defined as any grade 3 or higher adverse events (according to NCI CTCAE v5.0) related to study treatments at any point within the follow up period following the administration of study treatments.

Feasibility (delay in surgery)

Feasibility or [REDACTED]

Patient's surgery is scheduled to take [REDACTED] following the administration of study treatment. [REDACTED]

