Hemoglobin	$\geq 10 \text{ g/dL}$
Renal*	
Serum creatinine OR Measured or calculated ^a creatinine clearance (GFR) can also be used in place of creatinine or CrCl)	$\leq 1.5 \times \text{ upper limit of normal (ULN)}$ OR $\geq 60 \text{ mL/min}$ for patient with creatinine levels $> 1.5 \times$ institutional ULN
Hepatic*	
Serum total bilirubin	$\leq 1.5 \times \text{ ULN}$ OR Direct bilirubin $\leq \text{ ULN}$ for patients with total bilirubin levels $> 1.5 \text{ ULN}$
AST and ALT	$\leq 2.5 \times \text{ ULN}$
Albumin	$\geq 2.5 \text{ mg/dL}$
Coagulation*	
International Normalized Ratio (INR) or Prothrombin Time (PT)	$\leq 1.5 \times \text{ ULN}$ unless patient is receiving anticoagulant therapy as long as PT is within therapeutic range of intended use of anticoagulants
Activated Partial Thromboplastin Time (aPTT)	$\leq 1.5 \times \text{ ULN}$ unless patient is receiving anticoagulant therapy as long as PTT is within therapeutic range of intended use of anticoagulants

^a Creatinine clearance should be calculated per institutional standard.

* If laboratory criteria are not met due to what the investigator determines to be a biologic cause (e.g. Gilbert's syndrome causing elevated bilirubin or excessive muscle mass affecting creatinine) or drug-related cause (e.g. elevating in transaminases due to HAART therapy, elevated INR due to anticoagulation) then the lab values will not be used to exclude patient from this trial. Similarly, for patients with elevated bilirubin due to biliary obstruction from tumor, this will not serve as an exclusion criterion. This determination will be made by PI.

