5.2.3 Safety laboratory parameters

Safety laboratory parameters will be analysed at a local laboratory. Safety laboratory examinations will include tests as listed in [Table 5.2.3:1](#) and should be obtained at the time points specified in the flow chart.

All analyses will be performed by the site's local laboratory, the respective reference ranges will be provided in the ISF.

Patients do not have to be fasted for the blood sampling for the safety laboratory.

Instructions regarding sample collection, sample handling / processing and sample shipping are provided in the Laboratory Manual (to be filed ISF).

The local laboratory will send reports to the investigator. It is the responsibility of the investigator to evaluate the laboratory reports. Clinically relevant abnormal findings as judged by the investigator will be reported as adverse events (please refer to section [5.2.6](#)).

In case the criteria for hepatic injury are fulfilled, a number of additional measures will be performed (please see section [5.2.6.1](#)) and the DILI Checklist provided in the ISF system. The amount of blood taken from the patient concerned will be increased due to this additional sampling.

The laboratory will transfer the results of the analysis to the sponsor or delegate.

Table 5.2.3:1 Safety laboratory tests

Category	Parameters
Haematology	Haemoglobin, haematocrit, platelet count, reticulocytes, red blood cell count, mean corpuscular volume, mean corpuscular hemoglobin, mean corpuscular hemoglobin concentration, erythrocytes distribution width, white blood cell count with differential (neutrophils, lymphocytes, monocytes, eosinophils, basophils) preferably expressed in absolute values.
Biochemistry	Glucose, sodium, potassium, chloride, calcium, magnesium, phosphate, venous bicarbonate HCO_3 , total protein, albumin, uric acid and creatinine kinase (CK; if CK is elevated, then CK-MB [cardiac], Troponin I or T, and myoglobin should be reactively tested). A thyroid panel (TSH, free T4, and free T3) will be done at the time of each standard biochemistry panel. If symptoms of pancreatitis are observed, amylase and lipase should be tested at the discretion of the Investigator.
Liver function	AST, ALT, alkaline phosphatase, lactate dehydrogenase, bilirubin (direct and indirect bilirubin in case of elevated total bilirubin values)

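### Section 7.2.6 sorts laboratory values by reference range and an undefined clinically relevant category, so a grade 3+ value not recorded as an AE would not be identified by grade

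*Protocol*

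**What the plan says.** Protocol Section 7.2.6 sets out two kinds of laboratory analysis: "Laboratory data will be analysed both quantitatively as well as qualitatively". On the qualitative part it says: "The latter will be done via comparison of laboratory data to their reference ranges". It continues: "Values outside the reference range as well as values defined as clinically relevant will be summarised". The arms are then compared descriptively on distribution parameters and on "frequency and percentage of patients with abnormal values or clinically relevant abnormal values". The section does not define a clinically relevant laboratory value, and it names neither a CTCAE grade nor a baseline shift for laboratory data.

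Three other parts of the protocol bear on this.

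- **Eligibility (Section 3.3.2, Table 3.3.2:1).** AST and ALT may be up to 2.5 x ULN. Creatinine and total bilirubin may be up to 1.5 x ULN, with alternative criteria above that. The footnote to the renal, hepatic and coagulation rows opens "If laboratory criteria are not met due to what the investigator determines to be a biologic cause", adds drug-related causes, and concludes "then the lab values will not be used to exclude patient from this trial".
- **Primary endpoint (Section 2.1.2).** "Safety is defined as any grade 3 or higher adverse events (according to NCI CTCAE v5.0) related to study treatments".
- **Route from laboratory value to AE (Section 5.2.3).** "Clinically relevant abnormal findings as judged by the investigator will be reported as adverse events".

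The final SAP (Sections 4 and 7.8.2) replaces the protocol's planned outputs with a patient profile listing that includes all laboratory data for the two treated patients.

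**The concern.** The primary question is related grade 3 or higher toxicity. Table 10.3:1 lists transaminase elevation, creatinine elevation and haematological events among the immune-related events of interest, so some of that toxicity would appear first as a laboratory value. Apart from the mandatory hepatic-injury rule, a laboratory value generally becomes an AE only when an investigator judges it clinically relevant. The trial is open-label and planned for a single centre, and the principal investigator is a decision maker on the DRC (Section 3.1.1). A laboratory summary on the same grading scale as the endpoint would be an independent check on that step. A summary by inside or outside the range is not, least of all for patients who were outside it at entry. If clinically relevant in Section 7.2.6 means investigator judgement, that category repeats the filter already applied to AEs.

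**Working it through.** This is mainly a comparison of passages. CTCAE laboratory cut-offs are not in the documents, so no grade is assigned to the examples below.

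**1. Does the range category move?** Inputs: the AST/ALT entry limit of 2.5 x ULN (Table 3.3.2:1) and the hepatic-injury levels for patients with AST and/or ALT above ULN at baseline (Section 5.2.6.1.4).

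| AST/ALT value | Fold rise from 2.5 x ULN | Range category | Hepatic-injury rule met? |
|---|---|---|---|
| 2.5 x ULN at entry | 1 | above | no |
| 5 x ULN, bilirubin below 2 x ULN | 5/2.5 = 2 | above | no |
| 5 x ULN, bilirubin at least 2 x ULN, same sample, causes due to underlying disease excluded | 2 | above | yes |
| 10 x ULN | 10/2.5 = 4 | above | yes |

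The range category is the same in every row. The rule closes the gap from 10 x ULN upward, or from 5 x ULN with the bilirubin criterion. An isolated rise between 5 and 10 x ULN is left outside it.

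**2. Other parameters.** The hepatic-injury rule does not cover creatinine, platelets or neutrophils. Creatinine can be above range at entry by the table's own terms. Platelets are admitted from 100,000/mcL and neutrophils from 1,500/mcL (1,000/mcL for African American patients). Whether those entry values are out of range depends on the local laboratory's ranges, which are kept in the investigator site file. That they can be is an assumption.

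**3. What else would show the value?**

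- *Quantitative summary (7.2.6).* The value enters the arm's distribution, but distribution parameters do not identify a patient or a grade.
- *Clinically relevant category (7.2.6).* It might capture the value, but with no criterion stated this cannot be determined.
- *AE tables (7.2.6).* They show severity, but only for events already recorded as AEs.
- *Table 10.3:1.* It has grade-based AESI triggers for transaminases and creatinine, but these generally depend on the event first being called immune-related. Grade 4 anaemia is an exception.

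**4. What one unrecorded event can do at a boundary.** Inputs from Section 7.2.3: prior Beta(0.1, 0.4), limit 20%, probability cut-off 85%. With x events in n patients the posterior is Beta(0.1 + x, 0.4 + n − x), and the quantity compared with 0.85 is P(rate > 0.20).

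| n | One below boundary | P | At boundary | P |
|---|---|---|---|---|
| 5 | 2: Beta(2.1, 3.4) | 0.807 | 3: Beta(3.1, 2.4) | 0.966 |
| 15 | 4: Beta(4.1, 11.4) | 0.695 | 5: Beta(5.1, 10.4) | 0.866 |
| 25 | 7: Beta(7.1, 18.4) | 0.809 | 8: Beta(8.1, 17.4) | 0.909 |

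This reproduces the plan's boundaries of 3, 5 and 8. When the recorded count is exactly one short, one unrecorded related event reverses the result. At 25 patients this is the final assessment, since Table 7.2.3:1 marks that row as the final sample size and not as an early stop. The figures illustrate boundary cases only. They would hold for any missed event of any type, and the documents give no rate of unrecorded grade 3+ values from which to derive an expected effect.

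**The case against.** A reader might infer that laboratory data are judged only by reference range and that grade 3+ laboratory toxicity therefore goes unseen. The documents do not support that. Section 7.2.6 also plans a quantitative analysis and a clinically relevant category. Findings judged clinically relevant become AEs, are graded by CTCAE v5.0 (Section 5.2.6.1.5) and are tabulated by severity. An AE that begins before dosing and deteriorates counts as treatment-emergent. The composite and its boundaries are counted from AEs, so the range table feeds neither. An extreme example such as ALT of 12 x ULN is not missed either: it meets the 10 x ULN hepatic-injury criterion and must be reported as an AESI without exemption (Section 5.2.6.2.3).

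Three further objections have force. Section 7.2.6 relies on the sponsor's standard tables, which are not supplied and may include graded laboratory output. Scheduled standard laboratory tests after dosing occur only at V03 (flow chart; Sections 6.2.2 and 6.2.3), so worst post-dose grade is usually one scheduled value plus any unscheduled tests. And programmatic grading cannot decide relatedness, which the endpoint requires.

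All of this stands, and it narrows the point. It does not supply the missing check: outside the hepatic-injury rule, the stated plan has no step that compares laboratory values, by grade, with the AEs recorded.

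**Conclusion.** The concern holds in a limited form. As written, Section 7.2.6 uses a laboratory classification that does not respond to severe worsening in a patient already out of range, leaves clinically relevant undefined, and gives no graded cross-check on an endpoint expressed in CTCAE grades. A grade 3+ value that was not recorded as an AE, and that lies outside the hepatic-injury rule, would not be identified by grade.

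It would go too far to conclude that the primary endpoint is miscounted, or that the stopping rule would be expected to give a different answer. Nothing in the documents shows that any such value went unrecorded.

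The conclusion assumes that the unseen sponsor standards do not already include CTCAE-graded laboratory tables; if they do, a reference to them in Section 7.2.6 would largely settle the matter. The practical weight is now low. Only two patients were treated, the first look at about 5 per arm was not reached, and the final SAP lists all their laboratory values and plans no summary table.

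**What to change.** In protocol Section 7.2.6, grade the laboratory values already collected programmatically by CTCAE v5.0 and show worst post-dose grade by baseline grade for each arm. Keep the reference-range flag for parameters with no CTCAE scale, and state how a clinically relevant value is defined if that category stays. Baseline values should be available: standard laboratory tests are scheduled on Day 1, and Section 7.3 substitutes the screening value when baseline is missing.

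Before each DRC look and the final analysis, list every post-dose grade 3+ value that is worse than baseline and has no matching AE, and query it before the composite is counted. Relatedness remains the investigator's judgement.

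For the final SAP's two-patient listing, a CTCAE grade column and an AE-match flag beside the laboratory values are enough.

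The cost is some programming, a few lines of text and a few more data queries. No new samples or visits are needed.

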7.2.7 Other Analyses

Not applicable.

7.2.8 Interim Analyses

Two interim analyses are planned to assess safety and feasibility of the treatments. A Bayesian framework will be used to assess safety and feasibility after, approximately, 5 and 15 patients are treated in each arm. A Data Review Committee (DRC) will review the overall data along with the results from Bayesian calculation at interim.

7.3 HANDLING OF MISSING DATA

In general, no imputation will be performed on missing efficacy data. Missing baseline laboratory values will be imputed by the respective values from the screening visit. No other imputations will be performed on missing data although every effort will be made to obtain complete information on all AEs. For partial or missing AE onset and/or end dates, BI internal rules will be followed (see Reference Document [001-MCG-156 RD01 “Handling of missing and incomplete AE dates”](#))

7.4 RANDOMIZATION

No randomization will be performed. Patients will be assigned alternately (sequentially one by one) to either of the cohorts and will receive one-time either of the combination treatments.

7.5 DETERMINATION OF SAMPLE SIZE

No formal statistical assumption is used for the sample size calculation. A total sample size of 50 (25 in each arm) evaluable patients is planned to enroll in this trial. With a sample size of 25 patients in each arm, the study will have a very low probability (0.01) to wrongly declare that the study shows unfavorable “safety/feasibility” when the true rate is 10%, while it will have a high probability of 89% to identify a high true unfavorable “safety/feasibility” rate of 40% ([Table 7.5:1](#)).

The simulation was performed using the Shiny Application: Bayesian Toxicity Monitoring version 2.2.1.0.

Table 7.5:1

Operating characteristic, based on 10000 simulated trials, for Bayesian monitoring for unfavorable “safety/feasibility”

Scenario	True Rate of unfavorable “safety/feasibility”	Probability of Early Stop	Probability of Declaring unfavorable “safety/feasibility”	Average No of patients	Average No of unfavorable “safety/feasibility”	Observed rate of unfavorable “safety/feasibility”
1	0.1	0.01	0.02	24.72	2.47	0.10
2	0.2	0.18	0.21	22.57	4.51	0.22
3	0.3	0.50	0.60	18.31	5.49	0.35
4	0.4	0.79	0.89	13.88	5.55	0.47
5	0.5	0.94	0.98	10.55	5.27	0.57

For pathological response (PR), a weakly informative prior for PR as Beta (0.15, 0.85) along with an observed PR of 5 out of 25 patients will provide a posterior probability of 70% that PR rate is more than 15%.

Table 7.5:2

Posterior probability of true pathological response

# of observed PR out of 25	Posterior probability that (PR > 0.05)	Posterior probability that (PR > 0.10)	Posterior probability that (PR > 0.15)
4	0.97	0.78	0.49
5	0.99	0.91	0.70
6	0.99	0.97	0.85

8. INFORMED CONSENT, TRIAL RECORDS, DATA PROTECTION, PUBLICATION POLICY, AND ADMINISTRATIVE STRUCTURE

The trial will be carried out in compliance with the protocol, the ethical principles laid down in the Declaration of Helsinki, in accordance with the ICH Harmonized Guideline for Good Clinical Practice (GCP), relevant BI Standard Operating Procedures (SOPs).

Standard medical care (prophylactic, diagnostic and therapeutic procedures) remains the responsibility of the treating physician of the patient.

The investigator will inform the sponsor or delegate immediately of any urgent safety measures taken to protect the trial patients against any immediate hazard, as well as of any serious breaches of the protocol or of ICH GCP.

The Boehringer Ingelheim transparency and publication policy can be found on the following web page: trials.boehringer-ingelheim.com. The rights of the investigator and of the sponsor

with regard to publication of the results of this trial are described in the investigator contract. As a rule, no trial results should be published prior to finalisation of the Clinical Trial Report (CTR).

The certificate of insurance cover is made available to the investigator and the patients and is stored in the ISF.

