7.2.3 Primary objective analyses

The primary endpoint of the trial is a composite endpoint, safety and feasibility. Primary evaluation of safety and feasibility will be reported for all treated patients and will be measured as proportion of patients (along with 95% CI) who will meet the criterion of safety or feasibility (or both) defined in section 2.1.2. Safety and feasibility will be summarized separately for each arm.

In addition, safety and feasibility will be monitored, at interim and at final, using a Bayesian method. The incidence of complications after surgery for colorectal cancer is assumed approximately 20%. We consider that a neoadjuvant therapy with one of the regimens is not feasible if at least 20% of the patients with 85% or higher probability experience treatment related grade 3 or higher adverse events or have delay in surgery due to treatment related adverse events. Interim and final assessments for safety and feasibility will be conducted, separately, approximately after 5, 15 and 25 (final) patients being treated in each arm.

With a conservative prior probability of unfavorable “safety/feasibility” as Beta (0.1,0.4), the stopping boundaries are defined as seeing unfavorable “safety/feasibility” in ≥ 3 of first 5 patients, ≥ 5 of first 15, 8 or more out of 25 patients ([Table 7.2.3:1](#)). In case one arm needs to be closed due to unfavorable “safety/feasibility”, accrual to the remaining arm will continue. The calculation was performed using the Shiny Application: Bayesian Toxicity Monitoring version 2.2.1.0.

Table 7.2.3: 1 Early stopping boundary for unfavorable “safety/feasibility

# of patients (inclusive) per cohort	# of patients with related grade ≥ 3 AE or surgery delay	Decisions
5	3-5	Stopping
15	5-15	Stopping
25	8-25	Reached to final sample size

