4. CHANGES IN THE PLANNED ANALYSIS OF THE STUDY

Due to the early discontinuation of the study following the enrolment of only two patients, this TSAP will provide only a patient profile listing containing data collected for these individual patients rather than the statistical outputs and analyses described in the trial protocol (including amendments).

The rationale behind creating patient profiles lies in the absence of statistical summary outputs. With a population size of 2, utilizing patient profiles rather than statistical summary outputs will facilitate a more straightforward presentation of the minimal data regarding patient disease background and patient safety details.

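### Section 7.5 gives 0.01 as the chance of wrongly declaring unfavourable safety/feasibility at a true 10% rate; the table it cites gives 0.02, and the exact value is 0.0196 per arm

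*Protocol*

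**What the plan says.** Protocol section 7.5 (Determination of sample size) supports 25 patients per arm with two operating characteristics of the Bayesian monitoring rule, and cites Table 7.5:1 for them.

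- At a true rate of 10%: "the study will have a very low probability (0.01) to wrongly declare that the study shows unfavorable" safety/feasibility.
- At a true rate of 40%: a "high probability of 89% to identify a high true unfavorable" safety/feasibility rate.

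Table 7.5:1 reports 10,000 simulated trials. It has one column for the probability of early stop and a separate one headed "Probability of Declaring unfavorable" safety/feasibility. The two rows that matter begin as follows (true rate, early stop, declaring, average number of patients):

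- Scenario 1: "0.1 0.01 0.02 24.72"
- Scenario 4: "0.4 0.79 0.89 13.88"

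Section 7.2.3 (Primary objective analyses) defines the rule. Each arm is assessed on its own after about 5, 15 and 25 patients. The boundaries are at least 3, 5 and 8 patients with an event. They derive from a Beta(0.1, 0.4) prior and an 85% posterior probability that the event rate is at least 20%. If one arm closes, the other continues.

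SAP section 4 provides patient profile listings "rather than the statistical outputs and analyses described in the trial protocol", because the trial was discontinued after two patients were enrolled.

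**The concern.** The sentence is about wrongly declaring a regimen unfavourable, and the cited table has a column for exactly that. The text and that column disagree at a true rate of 10% (0.01 against 0.02) but agree at 40% (89% against 0.89). The two figures in the sentence therefore do not match the same column.

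The figure is the stated false-alarm rate of a rule that can close an arm, and it is offered in support of the sample size. If the text were right, the table would be wrong and the boundaries might be in doubt. If the table is right, the protocol understates the false-alarm rate in its own prose, and anyone reusing the design text would carry the wrong number forward.

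The sentence also speaks of the study as a whole, although the rule and the simulated figures apply to one arm.

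**Working it through.** **Inputs.** From section 7.2.3: looks at 5, 15 and 25 patients per arm; boundaries 3, 5 and 8; prior Beta(0.1, 0.4); threshold 85% for a rate of at least 20%. From section 7.5: true rates of 0.1 to 0.5; 10,000 simulated trials.

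**Step 1: do the boundaries follow from the rule?** With r events in n patients the posterior is Beta(0.1 + r, 0.4 + n − r). The posterior probability that the rate exceeds 0.20 is:

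| Look | At the boundary | One event fewer |
|---|---|---|
| n = 5 | 3 events: 0.9665 | 2 events: 0.807 |
| n = 15 | 5 events: 0.866 | 4 events: 0.695 |
| n = 25 | 8 events: 0.909 | 7 events: 0.809 |

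Each boundary is the smallest count that reaches 0.85, so the boundaries are correct.

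**Step 2: exact crossing probabilities at a true rate p = 0.10.**

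- Look at 5: P(X₅ ≥ 3) = 10(0.1)³(0.9)² + 5(0.1)⁴(0.9) + (0.1)⁵ = 0.00810 + 0.00045 + 0.00001 = 0.00856.
- Look at 15: sum over k = 0, 1, 2 of P(X₅ = k) × P(Bin(10, 0.1) ≥ 5 − k) = 0.59049 × 0.001635 + 0.32805 × 0.012795 + 0.07290 × 0.070191 = 0.01028.
- Look at 25: the same recursion, over paths that have not crossed at 5 or 15, gives 0.00075.

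Early stop = 0.00856 + 0.01028 = 0.0188.

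Declaring = 0.00856 + 0.01028 + 0.00075 = **0.0196 per arm**.

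Average number of patients = 25 − 20 × 0.00856 − 10 × 0.01028 = 24.73 (table: 24.72).

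**Step 3: does the same calculation reproduce the whole table?**

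| True rate | Early stop, exact (table) | Declaring, exact (table) | Average N, exact (table) |
|---|---|---|---|
| 0.1 | 0.0188 (0.01) | 0.0196 (0.02) | 24.726 (24.72) |
| 0.2 | 0.184 (0.18) | 0.215 (0.21) | 22.579 (22.57) |
| 0.3 | 0.505 (0.50) | 0.605 (0.60) | 18.319 (18.31) |
| 0.4 | 0.794 (0.79) | 0.893 (0.89) | 13.887 (13.88) |
| 0.5 | 0.944 (0.94) | 0.986 (0.98) | 10.557 (10.55) |

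The stated rule reproduces the table. Several entries look truncated rather than rounded: for example, all five average sample sizes, and the early-stop cell at 10%.

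**Step 4: can the 0.01 be reached another way?**

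- A single look at 25 with boundary 8 gives 0.0023.
- A false declaration in at least one of two independent arms gives 1 − (1 − 0.0196)² = 0.039.
- Early stop alone gives 0.0188.

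None of these rounds to 0.01.

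**Step 5: simulation error.** The standard error at 10,000 trials is √(0.0196 × 0.9804 / 10,000) = 0.0014. The chance that a simulated declaring rate falls below 0.015, and so rounds to 0.01, is about 0.0002. The chance that it falls below 0.02, and so truncates to 0.01, is about 0.61.

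**The case against.** The strongest defence is truncation. If the software cuts to two decimals, as the table suggests, the exact 0.0196 would itself print as 0.01. A separate run would then show 0.01 about 61% of the time and 0.02 about 39% of the time. On that view 0.01 and 0.02 are two displays of the same quantity, and calling the text half the true value overstates a display effect. This stands as a possible cause, and it is a reason not to assert that the figure was copied from the early-stop column. It does not rescue the sentence, which cites Table 7.5:1; that table prints 0.02.

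A second objection is that the per-arm reading is already clear. The sentence opens with 25 patients in each arm, section 7.2.3 assesses the arms separately, and no average sample size in the table exceeds 24.72. That is fair. Adding the words per arm is a clarification and does not correct a separate error.

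A third is that nothing depends on the number. Section 7.1 plans no formal hypothesis testing, section 7.5 says no formal statistical assumption is used for the sample size, and the correct value sits in the table the sentence cites. This also stands, and it limits the weight of the point.

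**Conclusion.** The concern holds and is minor. The text says 0.01, the table it cites says 0.02, and the exact value is 0.0196 per arm. The gap is about 0.01 in absolute terms. The paired 89% is correct (exact 0.893).

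The exact value assumes independent patients with a common event rate within an arm, and looks at exactly 5, 15 and 25 patients; the protocol says approximately. The close match to the table indicates that the sponsor's simulation used the same set-up. The origin of the 0.01 cannot be determined from the documents.

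The description of the probability as very low remains true at 0.02. The boundaries, looks, sample size and decisions do not change, and the SAP's listings for two patients make no use of the figure.

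**What to change.** In section 7.5, replace (0.01) with (0.02 per arm), and state that the 89% also applies to each arm separately. This changes one number and adds a few words; it needs no new simulation and alters no design element.

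Optionally, note under Table 7.5:1 that its entries appear truncated, or round the whole table consistently. Changing a single cell would create a new inconsistency.

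If the protocol will not be amended now that the trial has been discontinued, a correction note wherever the section 7.5 text is quoted or reused is enough.

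### Does Table 7.5:2 contradict the Beta(0.15, 0.85) prior stated for the pathological-response analysis?

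*Protocol*

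**What the plan says.** Protocol 7.2.4 sets the secondary analysis of pathological response. At the final analysis the "posterior probability, for each arm, that the PR rate is at least 15% will be calculated". The model and prior for this are also given there: "under the beta-binomial model with a weakly informative prior: Beta (0.15, 0.85").

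Protocol 7.5 uses the same model for planning, with "a weakly informative prior for PR as Beta (0.15, 0.85"). Its worked example takes 5 responders in an arm of 25, a result which, it says, "will provide a posterior probability of 70% that PR rate is more than 15" per cent. Table 7.5:2, titled "Posterior probability of true pathological response", then prints:

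| Responses out of 25 | PR > 0.05 | PR > 0.10 | PR > 0.15 |
|---|---|---|---|
| 4 | 0.97 | 0.78 | 0.49 |
| 5 | 0.99 | 0.91 | 0.70 |
| 6 | 0.99 | 0.97 | 0.85 |

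The same section gives 25 patients per arm but says that no formal statistical assumption lies behind that number. Protocol 7.1 states that no hypothesis is tested and that every analysis is descriptive and exploratory. SAP sections 4 and 7.5.2 record that only two patients were enrolled, that patient profile listings replace the statistical outputs, and that the secondary objective analysis will not be performed.

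**The concern.** The beta-binomial model is conjugate, so each cell of Table 7.5:2 is a single exact tail probability that any reader can check. Rounded to two decimals, the stated prior disagrees with six of the nine printed cells, and every one of the six is printed too low. A slightly different prior, Beta(0.1, 0.9), gives all nine printed values when the decimals are cut off. That pattern suggests the table was run with a prior other than the one in the text.

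If so, the planning figures and the planned analysis would belong to different models. The posterior probability that PR is at least 15% is the only efficacy quantity that the protocol links to a conclusion about activity. With 4 responses in 25, the printed value (0.49) lies below one half and the exact value (0.5047) above it.

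**Working it through.** **Inputs.** Prior Beta(a, b) with a = 0.15 and b = 0.85 (Protocol 7.2.4 and 7.5); n = 25 per arm and x = 4, 5 or 6 responses (Protocol 7.5 and Table 7.5:2); thresholds t = 0.05, 0.10 and 0.15 (Table 7.5:2).

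**Formula.** The posterior is Beta(a + x, b + n − x). Each cell is P(PR > t), the upper tail of that distribution.

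**The quoted 70%.** With x = 5 the posterior is Beta(5.15, 20.85), and P(PR > 0.15) = 0.7097. This rounds to 0.71 and truncates to 0.70, so the sentence in 7.5 can be reproduced by truncation.

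**All nine cells under the stated prior.**

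| x | Posterior | PR > 0.05 (printed) | PR > 0.10 (printed) | PR > 0.15 (printed) |
|---|---|---|---|---|
| 4 | Beta(4.15, 21.85) | 0.9726 (0.97) | 0.7901 (0.78) | 0.5047 (0.49) |
| 5 | Beta(5.15, 20.85) | 0.9944 (0.99) | 0.9156 (0.91) | 0.7097 (0.70) |
| 6 | Beta(6.15, 19.85) | 0.9991 (0.99) | 0.9720 (0.97) | 0.8562 (0.85) |

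**Rounded or truncated?** For x = 6 and t = 0.05 the exact value is 0.999 under the stated prior and also under Beta(0.1, 0.9). The table prints 0.99. Rounding would give 1.00, so truncation is the likelier convention.

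**Count of matching cells, with one convention applied to both priors.**

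| Prior | Matches by truncation | Matches by rounding |
|---|---|---|
| Beta(0.15, 0.85), as stated | 7 of 9 | 3 of 9 |
| Beta(0.1, 0.9) | 9 of 9 | 8 of 9 |

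The count of six wrong cells therefore holds only under rounding. Under truncation, the only convention by which the alternative prior matches every cell, two cells are wrong.

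**The two cells that fail either way**, both in the 4/25 row:
- PR > 0.10: 0.7901 − 0.78 = 0.0101, or 1.0 point.
- PR > 0.15: 0.5047 − 0.49 = 0.0147, or 1.5 points.

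**Can the cause be identified?** No.
- Beta(0.1, 0.9) gives 0.9705/0.7815/0.4936 for x = 4, 0.9939/0.9112/0.7007 for x = 5 and 0.9990/0.9703/0.8504 for x = 6. Beta(0.12, 0.88), Beta(0.1, 0.8), Beta(0.1, 0.85) and Beta(0.15, 1.1) also match all nine cells by truncation.
- The protocol does not say whether this table was computed exactly or simulated. If it was simulated (an assumption), the standard error of a probability near 0.5 is √(0.5 × 0.5 / N): 1.6 points with N = 1,000 draws and 0.5 points with N = 10,000. A gap of 1.5 points would be ordinary in the first case and unlikely in the second.
- The safety/feasibility prior in 7.2.3, Beta(0.1, 0.4), was not borrowed by mistake: it gives 0.5104 for 4/25 and PR > 0.15, further from 0.49.

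**The case for a change.** The strongest case for a correction is that the table does not follow from the prior printed just above it. The 0.49 cell is the firm evidence, since 0.5047 cannot become 0.49 by any two-decimal convention. Simulation error is a weak excuse: in simulations of the whole table under the stated prior, all nine cells matched by truncation in about 2% of runs at 5,000 draws and about 5% at 10,000, and in none at 1,000 or 100,000. A different prior is thus the likeliest explanation, and recomputing one small table would cost almost nothing.

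The arithmetic stands: two cells are wrong, and the stated prior does not produce them. What does not stand is the step from there to a contradiction in the plan. Whatever was used for the table, 7.2.4 alone governs the analysis. It names one prior and one threshold, 7.5 repeats both, and no rival PR prior appears in either document. An analyst working from the protocol would use Beta(0.15, 0.85).

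The crossing of one half at 4/25 has no consequence either, because the protocol attaches no posterior cut-off, at 50% or elsewhere, to pathological response. The operating characteristics offered for 25 per arm are those for safety and feasibility in Table 7.5:1; the PR table is an illustration.

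**Conclusion.** This is a clerical slip in an illustrative table. Two of nine cells are too low, by 1.0 and 1.5 percentage points; the quoted 70% and the other seven cells agree with the stated prior on truncation. That reading assumes that the table truncates, which the 0.99 printed for an exact 0.999 supports but does not prove. If the table was meant to be rounded, more cells differ, but the largest gap is still 1.5 points.

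Correcting the cells would alter no stopping boundary, sample size, analysis rule or conclusion: the prior and threshold for the analysis are stated consistently, no PR decision cut-off exists, and the sample size does not rest on this table. Nor can a reported result be affected, since under the SAP no PR posterior will be calculated for the two patients treated. The mismatch is real, but nothing is gained by changing the plan.
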